## Statistical Analysis Plan

Note: if “Is there a requirement for ventilatory support?”=“Yes” but ventilatory support used is Low Flow Nasal Cannula, this shouldn’t be considered as positive pressure use. Please refer to Data Review report for additional details.

### ***Mortality/BPD incidence***

The mortality/BPD incidence at 36-week PMA will be defined as:

Incidence of neonates dead within 36-week PMA or alive at 36-week PMA with a diagnosis of BPD.

### ***6.1.4.9      Rescue medication***

The percentage of patients requiring at least one rescue surfactant dose at any time during the study and within 48 hrs since last dose will be determined by treatment group. Patients with pulmonary hemorrhage during the study (displayed as adverse event with corresponding preferred term ‘Pulmonary haemorrhage’) will be excluded from this summary.

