8. EFFICACY ASSESSMENTS

- SpO₂/FiO₂ at 30 minutes, at 1, 3, 6, 12, 18, 24 hours, at Days 2, 3, 5, 7, 28±2 PNA, at discharge home and at 36 weeks PMA.

- Fraction of inspired oxygen (FiO₂) at 30 minutes, at 1, 3, 6, 12, 18, 24 hours, at Days 2, 3, 5, 7, 28±2 PNA, at discharge home and at 36 weeks PMA;
- Respiratory Severity Score (RSS) will be calculated from ventilator setting as FiO₂ x MAP in the 2 days post treatment (at 30 minutes, at 1, 3, 6, 12, 18, 24 hours and on day 2);
- Oxygen Saturation Index (OSI) will be calculated as FiO₂ x MAP x 100 / SpO₂ in the 2 days post treatment (at 30 minutes, at 1, 3, 6, 12, 18, 24 hours and on day 2);
- Arterial oxygen saturation determined by pulse oximetry (SpO₂) at 30 minutes, at 1, 3, 6, 12, 18, 24 hours, at Days 2, 3, 5, 7, 28±2 PNA, at discharge home and at 36 weeks PMA;
- Mean airway pressure (MAP) at 30 minutes, at 1, 3, 6, 12, 18, 24 hours, on Days 2, 3, 5, 7;
- Peak inspiratory pressure (PIP) at 30 minutes, at 1, 3, 6, 12, 18, 24 hours, on Days 2, 3, 5, 7;
- Positive end-expiratory pressure (PEEP) at 30 minutes, at 1, 3, 6, 12, 18, 24 hours, on Days 2, 3, 5, 7
- Alveolar-arterial (A-a) at 3, 6, 12, 18, 24 hours and 2 days post treatment (only in a subgroup of babies when feasible).
- Oxygenation Index (OI) at 3, 6, 12, 18, 24 hours and 2 days post treatment (only in a subgroup of babies when feasible).
- Mortality/BPD rate defined as the incidence of patients who are dead or alive with a diagnosis of BPD at 36-week PMA;
- BPD incidence at 36-week PMA;
- Mortality rate at Day 28 PNA and 36-week PMA;
- RDS-associated mortality rate through 14 days of age, defined as deaths associated with RDS through the first 14 days of life, resulting from severe respiratory failure, from pulmonary hemorrhage if the RDS had not resolved before the development of this complication, or from air leaks that occurred in the presence of severe RDS;
- Percentage of patients requiring at least one surfactant rescue dose;
- Percentage of patients with at least one reading of FiO₂=0.21 (i.e. room air) within 24 hours from first dosing with test treatment;
- Time (hours) to reach FiO₂=0.21 (i.e. room air);
- Duration of invasive mechanical ventilation, defined as the time until the first successful extubation lasting more than 24 hours (days);

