10.8 Recording Adverse Events

All AEs occurring during the course of the study must be documented in the Adverse Event page of the eCRF. Moreover, if the Adverse Event is serious, the Serious Adverse Event Form must also be completed.

It is responsibility of the Investigator to collect all adverse events (both serious and non-serious). As a general rule, the recording period for Adverse Events is the period starting from the Informed Consent signature until the subject's study participation ends. However, **the complications of prematurity**, listed below, are clinically expected outcomes in preterm neonates aged between 24⁺⁰ and 29⁺⁶ weeks. Therefore, **if started before drug administration, they haven't to be reported as AEs but in the relevant section of the eCRF**. While **the occurrence or worsening of these complications of prematurity after test treatments' administration must be recorded as an AE in the case report form**.

Morbidities or Complications of prematurity

- Air leaks (pneumothorax, pneumomediastinum, pneumopericardium, pneumoperitoneum);
- anemia of prematurity;
- apnea of prematurity;
- necrotizing enterocolitis (NEC);
- patent ductus arteriosus (PDA);
- pneumonia;
- pulmonary interstitial emphysema (PIE);
- pulmonary hemorrhage;
- germinal matrix/intraventricular hemorrhage (GMH/IVH);
- cerebral parenchymal haemorrhage;
- neonatal jaundice;
- periventricular leukomalacia (PVL);
- sepsis and/or meningitis;
- Presence of the following abnormal laboratory values:
 - hypoglycaemia
 - hyperglycaemia
 - hypocalcaemia
 - hypercalcaemia
 - hyponatraemia
 - hypernatraemia
 - hypokalaemia
 - hyperkalaemia.

For study definitions see appendix II and its references.

The investigator should carefully check inclusion and exclusion criteria because some of these morbidities may not allow the neonate to be randomized.

If a clinically significant abnormal laboratory finding or other abnormal assessment detected during the study period meets the definition of an AE, then the AE eCRF page must be completed, as appropriate. A diagnosis, if known, or clinical signs and symptoms if diagnosis is unknown, rather than the clinically significant abnormal laboratory finding, should be reported on the AE eCRF

page. If no diagnosis is known and clinical signs and symptoms are not present, then the abnormal finding should be recorded.

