- RSS will be compared between treatments at day 2 using linear mixed model including, treatment, investigational site and gestational age group as fixed effects.

Oxygen saturation index

- OSI, will be calculated as MAP x FiO₂ x 100/ SpO₂ and analyzed at each time point and averaged over the first 24 hours post study drug intake using the same model used for the SpO₂/FiO₂.

Time profile plot of mean OSI in the first 24 hours after treatment will be presented by treatment group.

- OSI will be compared between treatments at day 2 using linear mixed model including, treatment, investigational site and gestational age group as fixed effects.

SpO₂

- SpO₂ values as well as changes from baseline will be summarized at any post-treatment time point by treatment group by means of descriptive statistics.

MAP, PIP, PEEP

- MAP, PIP, PEEP values as well as changes from baseline will be summarized at any post-treatment time point by treatment group by means of descriptive statistics.

Duration of ventilation/oxygen use

- The median duration time (days) of invasive mechanical ventilation, oxygenation, non-invasive ventilation will be compared between treatment groups by using the Mann-Whitney U-test.

Mortality and BPD

- Mortality/BPD rate at 36-week PMA will be compared by treatment by means of Cochran-Mantel-Haenszel (CMH), adjusting for stratification factors (i.e. GA group and investigational site). Relative Risk (RR) and related 95% confidence interval will be provided.
- The incidence of BPD at 36-week PMA will be compared by treatment as for Mortality/BPD rate.
- The mortality rate at 36-week PMA and at Day 28 will be compared by treatment as for Mortality/BPD rate.
- RDS-associated mortality rate through 14 days of age will be compared by treatment as for Mortality/BPD rate.

Rescue surfactant use

The percentage of patients requiring at least one rescue surfactant dose will be compared by treatment group by means of a Fisher's exact test at 5% significance interval. Odds ratio (OR) and related exact 95% CI will be also provided. Patients with pulmonary haemorrhage will be excluded from this summary.

Biomarkers of inflammation

Mean values of biomarkers of inflammation (i.e., CXCL8, IL1 β , IL6, TNF- α , MPO) in the tracheal aspirates as well as change from baseline to 24 and day 2 (48 hours) will be summarized by treatment by means of descriptive statistics.

Alveolar-arterial gradient and Oxygenation Index

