### **6.2.2 Intention-to-Treat Population**

The Intention-to-Treat population (ITT) consists of all randomized patients who received at least one dose of study medication and with at least one available evaluation of efficacy after the baseline.

The efficacy analyses will be performed based on the ITT population.

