### 6.3.10 Exposure to the Investigational Medicinal Product

Drug dosing (both initial and re-dosing) information (dosing date/time, volume administered, calculated dose administered), if available, will be presented in a listing (Appendix 16.2.5).

First and cumulative dose as well as total dose administered (mg/kg) will be summarized by treatment. Number and percentage of neonates receiving additional study drug doses will be summarized by treatment, overall and by number of additional doses (1 or 2).

Time since birth to first dose (h) and to each of the additional doses (h) will be summarized by treatment.

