### 6.3.12.1.8 Rescue surfactant use

The percentage of patients requiring at least one rescue surfactant dose will be compared by treatment group by means of a Fisher's exact test at 5% significance interval. Odds ratio (OR) and related exact 95% CI will be also provided. Patients with pulmonary hemorrhage will be excluded from this summary.

For Fisher's exact test SAS code similar to this will be used:

```
PROC FREQ DATA = ...;
  WEIGHT count;
  TABLE treatment*result/measures riskdiff (CL=(WALD MN)) alpha=0.05
    exact fisher or / alpha=0.05;
  RUN;
/* option riskdiff (CL=(WALD MN)) gives the WALD CI and the CI based on inverting a score test,
as suggested by Miettinen and Nurminen (1985), but can be adapted if deemed appropriate */
```

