## Statistical Analysis Plan

\*Table 14.2.5 Summary of SpO2 (%) versus Time Point by Treatment (ITT Population)

Table 14.2.6 Summary of Ventilator Settings (MAP, PIP, PEEP) versus Time Point by Treatment (ITT Population)

\*Table 14.2.7 Mortality and BPD (ITT Population)

\*Table 14.2.8 Rescue Medication (ITT Population)

Table 14.2.9 Duration of Ventilation (ITT Population)

Table 14.2.10 Summary of Duration of Oxygen Use (ITT Population)

Table 14.2.11 Biomarkers (ITT Population)

Table 14.2.12 Summary of Alveolar-Arterial Gradient (A-aO2) (ITT Population)

Table 14.2.13 Summary of Oxygenation Index (OI) (ITT Population)

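### The only tested rescue-surfactant comparison drops every baby with a post-dosing pulmonary haemorrhage, so it is not the ITT comparison that its table label claims

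*SAP*

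**What the plan says.** The exclusion appears in four places. The protocol outline has it, and protocol 12.3.4 states "Patients with pulmonary haemorrhage will be excluded from this summary" directly after specifying Fisher's exact test with an odds ratio and exact 95% CI. SAP 6.3.12.1.8 does the same: "Patients with pulmonary hemorrhage will be excluded from this summary". SAP 6.1.4.9 gives the working definition: "Patients with pulmonary hemorrhage during the study (displayed as adverse event with corresponding preferred term" for pulmonary haemorrhage). It covers both rescue percentages defined there: at any time in the study, and within 48 hours of the last dose.

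Protocol 10.8 decides which haemorrhages become adverse events. A listed complication that began before dosing goes to a separate eCRF section; "the occurrence or worsening of these complications of prematurity after" study treatment is recorded as an AE. Pulmonary haemorrhage is on that list.

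On the population, SAP 6.2.2 says "The efficacy analyses will be performed based on the ITT population", and its ITT definition contains no haemorrhage condition. The SAP's list of outputs has "Table 14.2.8 Rescue Medication (ITT Population").

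One output has no exclusion. SAP 6.3.10 plans that "Number and percentage of neonates receiving additional study drug doses will be summarized by treatment". It is descriptive, sits in the exposure section, and is tabulated in the safety population.

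**The concern.** Because the exclusion is keyed to adverse events, it picks out haemorrhages that begin or worsen after the randomised treatment has been given. The babies left in each arm are no longer the groups that randomisation formed.

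The plan itself treats haemorrhage as an outcome. It is a reported neonatal morbidity, and the definition of RDS-associated death in protocol section 8 includes death "from pulmonary hemorrhage if the RDS had not resolved before the development of this complication". That is a cause-of-death rule and does not say that all haemorrhage reflects unresolved RDS. It does show that the event can belong to the disease course that the two surfactants are compared on.

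The rule also has no time limit. Protocol 7.1 allows up to two repeat doses at roughly 12-hour intervals, yet a haemorrhage weeks later still removes the baby from a question about early re-dosing.

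Need for re-dosing is the first secondary objective in protocol 2.2. If haemorrhage rates differ between arms, the exclusion can hide a real difference in rescue use or produce one that is absent among all babies.

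**Working it through.** **Tracing the rule.** Haemorrhage before dosing, not worsening: not an AE, so the baby stays. Haemorrhage starting or worsening after dosing, at any time: an AE, so the baby is removed. The tested denominator is therefore ITT minus post-dosing haemorrhages, under a table headed ITT.

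**Inputs from the documents.** 63 babies per arm (protocol 12.1); Fisher's exact test (SAP 6.3.12.1.8), two-sided at 5% (SAP 6.3.2). The documents state no rescue rate, haemorrhage rate or power, so there is no planned figure to reproduce. All rates below are assumptions.

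**Babies lost.** 126 × 5% = 6.3, 126 × 10% = 12.6 and 126 × 15% = 18.9.

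**Formulas.** Let q be the haemorrhage rate in an arm, a the rescue rate among haemorrhage babies, r the rate among the others, and R the overall rate. Then R = q·a + (1 − q)·r, so r = (R − q·a)/(1 − q). Rejection probability with the exclusion is the Fisher rejection probability at rates r, averaged over binomial haemorrhage counts in each arm (exact enumeration).

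**(1) No true difference: R = 30% in both arms.** The all-baby test rejects 3.3%. With the exclusion:

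| Haemorrhage, arm 1 v arm 2 | a = 50% | a = 60% | a = 80% |
|---|---|---|---|
| 5% v 5% | 3.8% | 3.8% | 3.8% |
| 10% v 5% | 4.1% | 4.3% | 5.1% |
| 15% v 5% | 4.7% | 5.8% | 9.7% |
| 20% v 5% | 5.9% | 8.8% | 19.7% |

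For 20% v 5% and a = 80%: r = (0.30 − 0.16)/0.80 = 17.5% v (0.30 − 0.04)/0.95 = 27.4%. The analysed babies differ although the arms do not.

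**(2) True difference: R = 38% v 19%, more haemorrhage in the higher-rescue arm.** All-baby power is 60%. With the exclusion:

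| Haemorrhage | a = 50% | a = 60% | a = 80% |
|---|---|---|---|
| 5% v 5% | 66% | 66% | 67% |
| 10% v 5% | 62% | 60% | 56% |
| 15% v 5% | 57% | 52% | 42% |
| 20% v 5% | 52% | 44% | 28% |

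**(3) The other construction: r = 30% in both arms.** The excluded analysis then targets OR 1.00 whatever happens among haemorrhage babies. With haemorrhage 15% v 5% and a = 80%, the all-baby rates are 0.15 × 0.8 + 0.85 × 0.3 = 37.5% and 0.05 × 0.8 + 0.95 × 0.3 = 32.5%. That is a difference of 5.0 points (OR 1.25) that the planned test cannot see. With haemorrhage 5% v 15%, it is −5.0 points.

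**(4) Count example.** All babies: 24/63 v 12/63, OR = (24 × 51)/(39 × 12) = 2.62, p = 0.029. Remove 8 v 2 haemorrhage babies, of whom 7 v 1 were rescued: 17/55 v 11/61, OR = (17 × 50)/(38 × 11) = 2.03, p = 0.130.

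**The case against.** The exclusion is pre-specified and disclosed in the protocol as well as the SAP, so it is not data-driven. The study is exploratory and unpowered, re-dosing is secondary, and no decision rule rests on this p-value.

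Much of the information is recoverable. Table 14.1.8.1 counts babies given additional study-drug doses without the exclusion, the AE and morbidity tables give haemorrhages by arm, and the all-randomised listings allow the two to be cross-tabulated.

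The illustrations depend on imbalance. At 10% v 5% the rejection rate is close to nominal, and at 5% v 5% the exclusion raises power. The large figures need a three- or four-fold difference in haemorrhage with most of those babies rescued, and table (2) looks at one direction only. Table (1) implies a real difference among the babies who did not bleed, so it is false only for the all-baby question.

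These points limit the size, and they stand to that extent. They do not remove the problem. Pre-specification prevents choosing the rule after seeing data; it does not restore a randomised comparison. The exposure count carries no test, odds ratio or interval, and covers study drug only, whereas protocol 7.1 records alternative surfactant as a concomitant medication. If rescue apart from haemorrhage is the intended question, the documents neither say so nor justify it, and the table label says otherwise.

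**Conclusion.** The concern holds. As written, the sole tested rescue comparison conditions on a post-dosing event while being presented as ITT, and no all-baby comparison is planned.

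The size cannot be determined from the documents. Under the assumed rates it ranges from negligible (haemorrhage about 5% in both arms) to a rejection rate of 9.7% instead of 3.3%, or power of 42% instead of 60%, at 15% v 5% with 80% of haemorrhage babies rescued. It is larger at 20% v 5%. The direction depends on which arm has more haemorrhage. Since arm rates are unknown when the rule is written, the main comparison should not depend on them. For an exploratory study and a secondary objective, this should be fixed but does not threaten the trial as a whole.

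**What to change.** In SAP 6.1.4.9 and 6.3.12.1.8, with matching wording in protocol 12.3.4 and the outline, base the main rescue comparison on all ITT babies, counting every rescue dose, with the same Fisher test, odds ratio and exact 95% CI. Keep the haemorrhage exclusion as a labelled sensitivity analysis, with its rationale. In Table 14.2.8, report for each arm the number excluded and how many of them received rescue surfactant. State also whether alternative surfactant counts as rescue in this table.

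The cost is wording and a few extra table rows. The dosing, concomitant-medication and AE data are already collected, and neither care nor the test changes.

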### ***6.1.4.10    Respiratory Support and Related Duration of Ventilation (Invasive and Non-invasive)***

Any respiratory Support given for the normal care of preterm neonates during the study conduct will be documented with:

- Was any respiratory support provided? (Y/N), if answered yes with:
- Method of Ventilation (and specification if other had been mentioned);
- Start/End Date and Time.

Non-invasive ventilation will include the use of at least one of the following ventilatory supports:

- Continuous Positive Airway Pressure (CPAP)
- Bi-level Positive Airway Pressure (BiPAP)
- Nasal Intermittent Positive Pressure Ventilation (NIPPV)
- High Flow Nasal Cannula (HFNC )
- Other: Nasal Synchronized Intermittent Positive Pressure Ventilation (nSIPPV)
- Other: Nasal Synchronized Intermittent Mandatory Ventilation (nSIMV)
- Other: Nasal Intermittent Mandatory Ventilation (nIMV)
- Other: Nasal High frequency ventilation (NHFV)
- Other: Nasal Pressure Support Ventilation (NPSV)

## Statistical Analysis Plan

- Other: NIPPV-NAVAMODE
- Other: NON-INVNAVA
- Other (refer to Data Review Report for exhaustive list)

Invasive ventilation will include the use of at least one the following ventilatory support:

- High Frequency Oscillatory Ventilation (HFOV)
- HFOV/NAVAMODE
- Synchronized Intermittent Mandatory Ventilation (SIMV)
- Patient Trigger Ventilation (PTV)
- Synchronized Intermittent Positive Pressure Ventilation (SIPPV)
- Other: Intermittent Mandatory Ventilation (IMV)
- Other: A/C (assist/control)
- Other: Pressure Support Ventilation (PSV)
- Other: PPVTHRUETTUBE
- Other: SIMV/NAVA,
- Other: IMV/NAVAMODE
- Other (refer to Data Review Report for exhaustive list).

Note: Low Flow Nasal Cannula use will be summarized under “Oxygen alone”.

Duration of non-invasive and invasive ventilation will be defined as total number of days when neonates received non-invasive and invasive mechanical ventilation, respectively.

Duration of ventilation (invasive and non-invasive) will be calculated as the sum of each period of received ventilation which will be calculated as ventilation end date/time minus ventilation started date/time. A review of these data will be performed during BDRM to specify whether specific adaptations of the algorithm have to be implemented.

To account for missing time in date/time when deriving duration variables, the following approaches will be used:

- Time points with unknown start and/or end times (but where the date is known) will be imputed with a time of 00:00 h or treatment administration time (1st treatment Day 1 only) for the tabulations but will be shown as NK:NK in the listings (where NK = Not Known).

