6.2.3 Administration

Before the administration of CHF 5633 or Poractant Alfa, the condition of the neonate should be stabilized, correcting any acidosis, hypotension, anaemia or hypothermia. The following modes and techniques for surfactant administration are the ones to be used in the present study:

- a. Disconnecting endotracheally intubated neonates from the ventilator, leaving the endotracheal tube

Disconnect the infant momentarily from the ventilator and administer the suspension, as a single bolus, directly into the lower trachea via the endotracheal tube. Perform approximately one minute of hand-bagging and then reconnect the infant to the ventilator at the same settings as before administration.

- b. Without disconnecting endotracheally intubated neonates from the ventilator

Administer the suspension, as a single bolus, directly into the lower trachea by passing a catheter through the suction port into the endotracheal tube or using an endotracheal tube with a side port.

- c. Infants stabilized on nasal continuous positive airway pressure (nCPAP) may also receive surfactant via an endotracheal tube solely introduced for the purpose of surfactant administration or with brief ventilation and rapid extubation. The tube is withdrawn after surfactant administration, and the infant is put on CPAP. If the condition of the baby worsens, standard of care measures could be applied at the discretion of the investigator

The CHF 5633 suspension will be withdrawn from the vial using a sterile syringe through a large-gauge needle (e.g., at least 20 gauge) and the effective dose calculated on the basis of the weight of the neonate could be administered as a single bolus dose or as two half bolus doses into the lower part of the trachea, positioning the neonate on each side as each bolus is being administered.

Since both test treatments will be refrigerated, each vial must be warmed up slowly to room temperature e.g. by placing it in an incubator for about 1 hour or keeping it in hands for 5-10 minutes and gently turned upside down, without shaking, avoiding the formation of foam. Artificial warming methods should not be used.

Re-treatment will be undertaken according to the criteria reported in Section 7.1. The exact time of the rescue treatment will be noted in the appropriate section of the eCRF.

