## Statistical Analysis Plan

dose of study drug month and year, and the end date (after any imputation) is on or after the first dose of study drug, then assume the date of the first dose of study drug. If the month and year are the same as the first dose of study drug month, and year and the end date (after any imputation) is prior to the first dose of study drug, then assume the end date for the onset date.

- DD-UK-YYYY/UK-UKN-YYYY: If the year is different from the year of first dose of study drug, assume 01-JAN-YYYY of the collected year. If the year is the same as the first dose of study drug year, and the end date (after any imputation) is on or after the first dose of study drug, then assume the date of the first dose of study drug. If the year is the same as the first dose of study drug, and the end date (after any imputation) is prior to the first dose of study drug, then assume the end date for the onset date.

Missing end dates (where UK and UKN indicate unknown or missing day and month respectively):

- UK-MMM-YYYY: Assume the last day of the month;
- DD-UKN-YYYY/UK-UKN-YYYY: Assume 31-DEC-YYYY.

Missing start/end time (where UK and UKN indicate unknown or missing day and month respectively):

- Adverse events with unknown start and/end times (but where the date is known) will be imputed with a time of 00:00 h (start) / 23:59 h (end) for the tabulations but will be shown as UK:UK in the listings (where UK = unknown). If the date is the date of treatment start will be imputed as time of start of treatment following a worst case approach.
- Adverse events with completely unknown start dates will be considered as treatment-emergent for the tabulations and will be shown as UK in the listings.

AE Duration (days) will be computed as follows:

- When both dates are completely known and AE is resolved:

$$\text{Duration (days)} = \text{AE end date} - \text{AE onset date} + 1$$

- When the AE onset date is fully known but the AE is not resolved at the end of the trial:

$$\text{Duration (days)} = \text{date of completion/discontinuation} - \text{AE onset date} + 1$$

In this case the duration will be presented as “>x days” in the listings rather than “x days”

When the AE onset date is incomplete or unknown or when the AE has resolved but with an incomplete or unknown end date, the AE duration will not be calculated, unless otherwise specified.

Chiesi

Final 1.0

CCD-5633AA1-02

18/July/2018

TP-EP.BS-WW-001-05

Effective date: 29 Jul 15

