## Statistical Analysis Plan

### ***6.1.4.11 Oxygen Use and Related Duration***

Any Oxygen given alone for the normal care of preterm neonates during the study conduct will be documented with:

- Was the subject given Oxygen alone? (Y/N), if answered yes with:
  - Start/End Date and Time.

In addition, all the cases of “Low Flow Nasal Cannula” as reported in the ventilatory parameters pages will be summarized under Oxygen use.

Duration of oxygen use will be calculated as sum of oxygen use/LFNC end date/time minus oxygen/LFNC use started date/time.

To account for missing time in date/time when deriving duration variables, the following approaches will be used:

- Time points with unknown start and/or end times (but where the date is known) will be imputed with a time of 00:00 h or treatment administration time (1st treatment Day 1 only) for the tabulations but will be shown as NK:NK in the listings (where NK = Not Known).

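### Unknown end times of ventilation and oxygen periods are set to 00:00 (or first-dose time on Day 1), so affected same-date periods can become zero or negative and longer ones lose up to 24 h

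*SAP*

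**What the plan says.** SAP 6.1.4.10 (ventilation) gives the rule "Time points with unknown start and/or end times (but where the date is known) will be imputed with a time of 00:00 h", followed by "or treatment administration time (1st treatment Day 1 only) for the tabulations". SAP 6.1.4.11 (oxygen alone and low-flow nasal cannula) repeats it. Neither section limits the Day 1 alternative to start times.

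For each ventilation period the SAP takes a difference, "which will be calculated as ventilation end date/time minus ventilation started date/time", and then adds up: "Duration of ventilation (invasive and non-invasive) will be calculated as the sum of each period of received ventilation". Oxygen is handled alike: "Duration of oxygen use will be calculated as sum of oxygen use/LFNC end date/time minus oxygen/LFNC use started date/time". Neither section sets a floor, a same-date exception or an exclusion.

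SAP 6.3.12.1.9 compares the durations by Mann-Whitney test with a Hodges-Lehmann interval. SAP 6.3.2 sets all tests two-sided at 5%. The results go into Tables 14.2.9 and 14.2.10.

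For ventilation, 6.1.4.10 adds: "A review of these data will be performed during BDRM to specify whether specific adaptations of the algorithm have to be implemented". Section 6.1.4.11 has no counterpart. For adverse events the same SAP (6.1.3.1.1) separates the two ends: missing times "will be imputed with a time of 00:00 h (start) / 23:59 h (end) for the tabulations".

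**The concern.** For a start time, 00:00 is the earliest possible value, so it can only lengthen a period. For an end time it is also the earliest possible value, so it can only shorten one, and on the start date it falls at or before any start. The Day 1 alternative has the same weakness for support that begins after the first dose.

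Oxygen requirement and ventilatory support make up the first main objective, and these durations are tested. A negative duration is impossible. Inside a sum it also cancels time the baby really spent on support.

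Short periods are foreseeable. Protocol 6.2.3 allows surfactant through an "endotracheal tube solely introduced for the purpose of surfactant administration or with brief ventilation and rapid extubation", and Protocol 7.1 allows up to two repeat doses about 12 hours apart. A brief re-dosing intubation later on Day 1 is therefore exposed. So are short oxygen-alone periods, because each occurrence is recorded separately.

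**Working it through.** The documents give no figure on this point to reproduce. The check applies the SAP rule to worked cases and then to assumed distributions.

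**Inputs.** Imputed end time: 00:00 of the end date, or first-treatment time on Day 1 (SAP 6.1.4.10, 6.1.4.11). Period = end minus start. Tested value = sum of periods per baby. Arm size: 63 (SAP section 4). The clock times below are illustrative.

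**Single periods, end time unknown, in hours**

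| Case | True | SAP rule |
|---|---|---|
| A. Not Day 1, 08:00 to 14:00 same date | 6 | 0 − 8 = −8 |
| B. Same date, start also unknown | not known | 0 − 0 = 0 |
| C. Day 1, dose 06:00, support 09:00 to 20:00 | 11 | 6 − 9 = −3 |
| D. Day 1, dose 06:00, support 02:00 to 20:00 | 18 | 6 − 2 = +4 |
| E. 08:00 to 14:00 next date | 30 | 24 − 8 = +16 |
| F. 08:00 to 14:00 ten dates later | 246 | 240 − 8 = +232 |

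A value at or below 0 needs a start and end on the same date. On Day 1 it also needs a start at or after dosing (C), or an unknown start. With a known start and a later end date (E, F; end date not Day 1), the loss equals the true end clock time: 0 to 24 h, and 12 h on average if that time is uniform.

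**Per-baby sums.** Take a first dose at 06:00 and a re-dosing intubation at 17:55 on the same date with an unknown end. The period becomes 06:00 − 17:55 = −11 h 55 min (−11.92 h).
- If the only other invasive period is a recorded 05:50 to 06:10 intubation (+0.33 h), the total is 0.33 − 11.92 = −11.59 h.
- If the other period is a recorded 72 h, the total is 72 − 11.92 = 60.08 h, which is too short but positive.

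**Share of affected periods at or below 0.** Assume a known start, uniform over the day, and the 00:00 rule.
- Fixed true length L below 24 h: share = 1 − L/24. This gives 92%, 75% and 50% for 2, 6 and 12 h.
- Exponential true length with mean m: share = 1 − (m/24)(1 − e^(−24/m)). For m = 6, 12, 24, 48, 120 and 240 h this gives 75.5%, 56.8%, 36.8%, 21.3%, 9.4% and 4.8%. Simulation agrees within 0.1 percentage point or so.

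**Effect on the test.** Simulated under no treatment difference: 63 per arm, one period per baby, exponential lengths, the 00:00 rule, 2,000 runs (Monte Carlo standard error about 0.005).

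| End times missing, by arm | Mean 24 h | Mean 72 h |
|---|---|---|
| None | 0.047 | 0.048 |
| 10% and 10% | 0.058 | 0.047 |
| 20% and 20% | 0.051 | 0.061 |
| 5% and 20% | 0.076 | 0.054 |

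Equal missingness leaves the type I error near nominal. Only the unequal case with short durations moves it clearly. Setting ends to 23:59 gives 0.080 in that same cell, so the adverse-event rule alone is no better there: it turns a mean error of about −12 h into about +12 h.

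**The case against.** The strongest reply is that this may rarely matter. The protocol requires changes of ventilation to be recorded with dates and times, and oxygen-alone periods with start and end (7.1.2 onwards). Edit checks look for incomplete data (section 11). The ventilation algorithm may be adapted at the blind review, and SAP 6.3.4 sends critical missing data there in general terms. The study is exploratory, and the duration tables are not marked for the Key First Results. All of this stands and limits the weight of the point. It does not repair the rule: the review sentence names no alternative and covers ventilation only.

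Three stronger readings are tempting, and the documents do not support them.

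- **That first-dose intubations become negative.** The tube goes in before the dose, so under the Day 1 rule an unknown end gives a positive value. Intubation at 10:00 and dosing at 10:10 gives +10 min. Later re-dosing intubations are the exposed ones.
- **That a ventilated baby would rank below one never ventilated.** This needs never-ventilated babies to enter the test as 0. The SAP does not say whether they do.
- **That the tests are generally invalid.** The tested value is a sum, so one negative period often only lowers a positive total. Nothing in the documents suggests that missing end times would differ between arms in this double-blind trial.

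The adverse-event rule shows that the SAP separates start and end elsewhere. It does not prove that the single rule here was a slip.

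**Conclusion.** The point holds in limited form. As written, the rule gives zero or negative durations for same-date periods with an unknown end time, subject to the Day 1 condition, and shortens periods with a known start and a later end date by up to 24 h. The 12 h average assumes end times uniform over the day. The shares at or below 0 further assume a uniform known start and the stated length distributions. These values lower the per-baby sums that are tested and tabulated.

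The consequence is impossible values and downward bias in the affected periods. A gross inflation of type I error is not shown: the highest simulated figure, about 0.08, needs an assumed 5% against 20% imbalance. The frequency of missing end times is not stated, so the practical effect could be negligible. A change is still warranted, because the fault lies in a stated rule, is cheap to remove, and has no specific safeguard for oxygen.

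**What to change.** Give separate start and end rules in SAP 6.1.4.10 and 6.1.4.11.

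1. **Unknown start.** Use 00:00, or first-treatment time on Day 1, but never later than the recorded end of that period. Where dosing time would be later, use 00:00, or time of birth if that is later. Without this limit, Day 1 support ending at 05:00 with dosing at 08:00 gives 5 − 8 = −3 h.
2. **Unknown end.** Use the recorded start of the next support mode on that date. If there is none, use a midpoint within the end date only. Its lower bound is the later of 00:00 and the period's start (imputed first if unknown). Its upper bound is the earlier of 23:59 and death or discharge.
3. **Check.** Require every period to be at least 0.
4. **Report.** Give the number of imputed periods per arm with Tables 14.2.9 and 14.2.10.

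With no later mode on the end date, and 23:59 = 23.98 h, the worked cases become:
- A: (23.98 − 8)/2 = 7.99 h
- B: 23.98/2 = 11.99 h
- C: (23.98 − 9)/2 = 7.49 h
- D: (23.98 − 2)/2 = 10.99 h
- E: 16 + 11.99 = 27.99 h
- F: 232 + 11.99 = 243.99 h

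The midpoint must stay within the end date. Taken from the period's start it would halve long periods. For a brief re-dosing intubation the next-mode rule should usually apply, since Protocol 6.2.3 returns such babies to CPAP.

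The cost is a few sentences and minor programming. The downside is a residual imputation error, at most about 12 h either way per period and near zero on average for periods ending on a later date if end times are uniform.
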